Effects of DASH Groceries on Blood Pressure in Black Residents of Urban Food Deserts With Treated Hypertension (GoFreshRx)

Short Title: Groceries for Black Residents of Boston to Stop Hypertension

PROTOCOL Version 1.6

August 11, 2025

SUMMARY OF MAJOR PROTOCOL VERSIONS AND CHANGES

Version 1.0

 Original version submitted to the Beth Israel Deaconess Medical Center Institutional Review Board on March 2, 2022.

Version 1.1

- Version 1.1 submitted to the Beth Israel Deaconess Medical Center Institutional Review Board on June 24, 2022.
- Change: Reduced laboratory exclusion criteria of potassium from ≥5.2 to ≥5

Version 1.2

- Version 1.2 submitted to the Beth Israel Deaconess Medical Center Institutional Review Board on August 22, 2022.
- Change: Clarified exclusion related to "Extreme Food Insecurity"

Version 1.3

- Version 1.3 submitted to the Beth Israel Deaconess Medical Center Institutional Review Board on December 28, 2022.
- Change: Extended eligibility to East Boston, Everett, Jamaica Plain, Malden, and Roslindale, reflecting recent data on neighborhoods with few grocery stores.

Version 1.4

- Version 1.4 submitted to the Beth Israel Deaconess Medical Center Institutional Review Board on February 3, 2023.
- Change: Increased family size from 3 to 5 adults

Version 1.5

- Version 1.5 submitted to the Beth Israel Deaconess Medical Center Institutional Review Board on February 17, 2023.
- Change: Revised the safety response for diastolic blood pressure at SVa from ≥100 mm Hg to ≥105 mm Hg to align with systolic blood pressure and screening procedures.

Version 1.6

- Version 1.6 submitted to the Beth Israel Deaconess Medical Center Institutional Review Board on November 16, 2023.
- Change: Updated family size eligibility from 5 adults to 6 at dinner time

GoFreshRx Protocol Table of Contents

1. ABSTRACT	5
2. SPECIFIC AIMS	6
3. BACKGROUND	7
4. OVERVIEW OF DESIGN	9

13. ANALYSIS	
Power and sample size	
Trial-wide data release	
16. TIMELINE	39
17. REFERENCES	40

LIST OF ABBREVIATIONS / GLOSSARY

ABPM Ambulatory Blood Pressure Monitoring
AOBP Automated Office Blood Pressure
BIDMC Beth Israel Deaconess Medical Center

BMI Body Mass Index Blood Pressure

CAB Community Advisory Board

CRC Clinical Research Center (at BIDMC)

CVD Cardiovascular disease

DASH Dietary Approaches to Stop Hypertension

DIGO Diet Gout Trial

DBP Diastolic Blood Pressure

DSMB Data Safety and Monitoring Board

GTE Getting to Equity FV (1-3) Follow-up Visit

GOFRESH Groceries for Black Residents of Boston to Stop Hypertension Trial

GO Grocery ordering calls

HIPAA Health Insurance Portability and Accountability Act

HR Heart rate HTN Hypertension

NIHMD National Institute of Minority Health and Health Disparity

IRB Institutional Review Board
OH Orthostatic Hypotension
PS Pre-Screening Visit

PRISM Practical Robust Implementation Sustainability Model

RE-AIM Reach, Effectiveness, Adoption, Implementation, Maintenance

[Implementation Framework]

RZ Randomization Visit

SDOH Social Determinants of Health

SNAP Supplemental Nutritional Assistance Program

SBP Systolic blood pressure

SV (a & b) Screening Visit

USDA US Department of Agriculture

1. ABSTRACT

Over **103 million adults** in the US have hypertension (HTN)¹ a major contributor to coronary heart disease and early death.² The rising prevalence in HTN is driven by increased consumption of high sodium, processed foods,³ which is particularly rampant among low-income urban communities that are disproportionately Black.⁴ Diet is the most substantial determinant of rising racial disparities in HTN risk,^{4,5} highlighting a critical need for innovative solutions to overcome barriers to healthy eating among Black adults in the US. Our proposal tests a dietitian-assisted, technology-based DASH grocery intervention to improve access to and consumption of a DASH eating plan among Black adults in the Boston area urban food deserts. The intervention will provide (1) three months of DASH-patterned groceries, (2) basic and scalable online skills in DASH grocery shopping using a web-based home-delivery platform and training in food storage and preparation, and (3) information on local venues (co-ops, stores, and food pantries) where participants can source healthy foods long-term at lower cost. This study will establish the effectiveness of home-delivered DASH groceries sufficient to meet dietary needs to reduce blood pressure (BP) and improve cardiovascular risk factors. Moreover, we will identify facilitators and barriers to maintenance of DASH adherence and home meal preparation.

2. SPECIFIC AIMS

Aim 1: Determine the effectiveness of dietitian-assisted, virtually ordered, home-delivered DASH groceries on systolic BP (SBP) among Black adults with treated stage 1 or 2 hypertension. H1.1 DASH groceries will lower SBP (primary outcome) compared to self-directed grocery shopping after 3 months and effects will be maintained at 6 months post-randomization.

Aim 2: Determine the immediate and sustained effects of dietitian-assisted grocery shopping on families' adoption of the DASH eating plan and frequency of home-prepared meals versus out-of-home dining, 3-, 5-6, and 12-months post-randomization. H2.1 DASH groceries will \uparrow DASH adherence (self-report, \downarrow urine sodium & \uparrow potassium) and H2.2 \uparrow home-prepared meals and \downarrow out-of-home dining (self-report, quantified using the SHoPPER questionnaire).

Aim 3: Evaluate the reach, maintenance, and cost-effectiveness of the intervention up to 12 months post-randomization using a RE-AIM framework and mixed methods. *H3.1*: Reach, quantified during our recruitment campaign, will be high. *H3.2*: A 3-month, dietitian-assisted program will be cost-effective compared to self-directed grocery shopping at 10 years. *H3.3*: Identifying barriers and facilitators in qualitative interviews will enhance scalability.

3. BACKGROUND

The DASH eating plan is a balanced eating plan rich in fruit, vegetables, low-fat dairy, and lean meats that is reduced in red meat, sweets, and sugary beverages.^{6,7} A reduced sodium, DASH eating plan has been demonstrated in randomized trials to lower BP⁸ within four weeks⁹ and is endorsed by the American Heart Association (AHA).¹⁰ Notably, the recipes in the original DASH trials were modeled after traditional American meals, dietary habits, and foods, using a one-size-fits-all approach,^{6,7} but implementation in a diverse range of urban cultural and ethnic groups has been limited.

Over the past 20 years, the average consumption of fruits and vegetables has remained between 1-2 servings/day,⁴ much lower than the 7-9 servings/day recommended in the DASH eating plan.⁸ While improvements in diet have been observed among higher income groups, the average number of servings of fruit and vegetables among the 42 million recipients of US food stamps (SNAP or Supplemental Nutrition Assistance Program) has stagnated at 1.3 servings/day.⁴ Lower diet quality is even more prevalent among Black versus White adults in urban areas.¹¹ The lower diet quality among Black adults is related to food insecurity, the inability to afford enough food for a healthy lifestyle,¹² and is experienced by 21% of Black (vs 16% of Hispanic and 8% of White) households.¹³ Several national studies have found strong associations between food insecurity and higher BP,¹⁴ worsening disparities in the prevalence of cardiometabolic diseases.¹⁵

Distance, cost, and cultural acceptability perpetuate dietary health disparities.¹⁶ Education is necessary but not sufficient to address disparities in healthy eating because of barriers to accessing healthy foods related to pervasive social determinants of health (SDOH). First, many Black adults live in urban food deserts, defined as communities characterized by lower income and a low concentration of local healthy grocery stores, such that fresh produce cannot be accessed without a car or public transportation.^{17,18} Second, DASH-like diets are costly,¹⁹ and price prevents their consumption among adults with low incomes and on food assistance,²⁰ perpetuating the experience of food insecurity. Finally, urban settings contain rich cultural and ethnic diversity with diverse eating patterns that may not align with the published DASH meals,²¹ despite attempts to translate to additional cultural groups.²²

Virtual grocery delivery is a promising innovation to mitigate the barriers outlined above. Prior studies showed that home delivery of DASH meals improved health.^{23,24} However, these studies relied on predetermined and fixed meals, which have limited generalizability to diverse groups and dietary preferences. In contrast, groceries can be prepared, adapted, or tailored to meet each person's taste, enabling adults to customize healthy eating to their own family traditions, a feature highlighted by some groups as essential for improved acceptability of DASH foods.²⁵ The sustainability of this strategy is supported by the US Department of Agriculture (USDA), which launched a SNAP virtual purchasing pilot, to add online grocery vendors to their

ecommerce platform, which has seen widespread expansion during the COVID-19 epidemic.²⁶ The USDA also recently launched a "Food Box" program to provide fresh produce, dairy, and meat groceries to families affected by COVID-19.²⁷

[figure not shown]
A growing number of food policy experts have advocated for grocery subsidies, ²⁸ with some recommending that SNAP be restricted to fruits and vegetables alone as a means of addressing health disparities. ^{29,30} However, there is limited evidence that the mere provision of healthy groceries would affect long-term change in dietary intake. In contrast, the 5+ Nuts and Beans trial demonstrated that dietitian-assisted grocery shopping, even when limited to the SNAP allotment of \$30/week, increased the number of fruit and vegetable servings consumed by urban-dwelling Black adults. ³¹ In a subsequent trial, we showed that dietitian-assisted DASH grocery shopping of \$105/week with Amazon Fresh (the Diet Gout [DIGO] trial) lowered urine sodium excretion over a 4-week period. ³² These two trials suggest that the provision of groceries coupled with mild skill acquisition does improve consumption of the DASH eating plan.

There is a critical need for a rigorous trial that demonstrates clinical effectiveness. While prior work demonstrated the ability of dietitian-assisted, DASH grocery interventions for changing behavior, neither study significantly affected clinical outcomes like BP or LDL-cholesterol. 31,33 Comparison of our two trials suggests that further replacement of participants' diets with study foods will achieve greater behavioral and clinical effects.

Translation and sustainability of the proposed intervention require a patient-centered focus that addresses SDoH. Even though the proposed intervention will improve access to healthy foods via grocery delivery, other contextual factors such as family dynamics, SDoH (e.g., food insecurity, lack of transportation), community norms and resources, culture, and even local or state level policies related to nutrition may affect continued consumption of the DASH eating plan. Using qualitative methods, we will evaluate the facilitators and barriers to sustaining the DASH eating plan among Black adults with Stage 1 or 2 HTN living in food deserts and the failure or success of the intervention from the participants' perspective.

[figure not shown]
Findings from the proposed study will provide the evidence needed for policy makers to evaluate the long-term impact of addressing the adoption of the DASH eating plan in low-income populations. As more states and the USDA consider using SNAP benefits to purchase online groceries especially in the wake of COVID-19, our proposal has the potential to change national SNAP policies to sponsor a DASH-patterned grocery program if the intervention is effective and can be implemented at an affordable cost.²⁹

4. OVERVIEW OF DESIGN

This project is guided by the National Institute of Minority Health and Health Disparities (NIMHD) health equity research framework while its evaluation will be guided by the RE-AIM implementation framework.^{34,35} specifically, the NIMHD framework will be used to evaluate the impact of a multilevel intervention (dietitian-assisted, technology-based DASH groceries) to improve access to and consumption of a DASH eating plan by Black adults in Boston area food deserts (**Figure 1**). We will use RE-AIM to evaluate the reach, adoption, maintenance, and cost-effectiveness of the intervention to inform broader scalability (see section 7 for details related to the implementation aims).

Using a Hybrid Type I effectiveness-implementation design, we will randomly assign 150 Black adults with treated stage 1 or 2 HTN to one of two 3-month lifestyle interventions: (1) Dietitian-assisted, virtually-ordered, home-delivered groceries consistent with the DASH eating plan or (2) Self-directed grocery shopping. The study has an intervention phase and a post-intervention maintenance phase. During the intervention phase, we will perform a randomized controlled trial with two parallel arms (**Figure 2**).

Aim 1 focuses on outcomes measured at the beginning and end of the intervention phase (3-months post-randomization) and 6-months post-randomization during the post-intervention maintenance period. The primary outcome is office systolic BP (SBP). Secondary outcomes are office DBP, wake-time 24-hour SBP and diastolic BP (DBP), high-density lipoprotein cholesterol, low-density lipoprotein cholesterol, triglycerides, and hemoglobin A1c. Aim 2 focuses on determining the effect of the intervention on DASH adherence (adoption) based on self-report and 24-hour urine electrolytes at 3- and 6-months post-randomization. We also determine meal preparation and dining practices at 3-, 6-, and 12-months post-randomization. Aim 3 will evaluate the reach, maintenance, and implementation (cost-effectiveness) of the intervention over the entire 12-month study using a RE-AIM framework.

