6. RECRUITMENT

BIDMC Clinical Research Center

The trial study assessments will be conducted at the BIDMC Clinical Research Center (CRC), Bowdoin Street Health Center, or at a clinical office where the PI and his team currently practice within the greater BIDMC health network, as approved by our IRB in Boston, Massachusetts.

The Clinical Research Center is a research facility within BIDMC that maintains contiguous space for inpatient, outpatient, and administrative activities. The outpatient area consists of 12 rooms with 2 of these equipped with beds and private bathrooms. The unit staff includes nurses, patient care technicians, dietitians, dietary support staff, a laboratory assistant, and a practice coordinator. The unit is open for patient activity 24 hours per day, 7 days per week. In addition, the Sample Processing Laboratory Service processes samples for analysis at various laboratories, including Quest Diagnostics. Samples are stored at room temperature or in a monitored and alarmed refrigerator, -20 C freezer short-term or -80 C freezer for long-term storage.

Recruitment strategies

We will implement a variety of strategies to achieve our recruitment target, i.e., ~176 participants. Our experience is that multiple strategies work synergistically to promote study name-brand recognition to enhance recruitment. We will employ the following approaches:

- (1) Website with information on the trial and GoFreshRx team members, as well as embedded Qualtrics form for sign up. The website is accessibility optimized. Sign up is built into the site and information will be directly sent to the [contact] email.
- (1) Flyers placed in the clinic waiting areas and flyer boards in the zip codes of interest with phone number, website, and QR code options.
- (2) Direct mail of study brochures to BIDMC patients and Boston area residents in the ZIP codes of interest who identify as Black/African American. We will purchase community-based lists of Black/African American adults living in the Boston zip codes of interest. In addition, we will identify BIDMC patients through the BIDMC Insight Core based on zip code and race/ethnicity. These individuals will receive a study brochure with business reply mail as well as information on how to contact the study team via phone, web, or email.

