Recruitment of women and Black adults

We will recruit 176 participants, anticipating a potential 15% attrition rate. We will recruit a population that is ~50% women and 100% Black. In order to achieve this goal, we will be tracking our recruitment goals on a weekly basis and making sure we are careful with our enrolment diversity in terms of gender.

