13. ANALYSIS

The trial has sufficient resources to enroll 150-176 participants who will be randomly allocated to 1 of 2 sequences for each of the two groups: (1) the Self-Directed group or (2) the DASH intervention group.

Power and sample size

A. Aim 1 Immediate Effects: Clinical Outcomes (Effectiveness)

- 1. Primary endpoint: The proposed study is powered for office SBP. Based on the 12-week SBP means and variances from the DASH-Sodium trial,⁶ with 75 people in each arm, we will be able to detect a difference in SBP of -5.8 mm Hg (type 1 error of 0.05, power of 0.85). The 12-week between-group difference in SBP in DASH-Sodium was -8.9 mm Hg.
- 2. Secondary endpoints: We will have adequate power to detect small differences (i.e., <15%) in awake-time SBP, BMI, cholesterol, triglycerides, and hemoglobin A1c.
- B. Aim 2 Immediate Effects: Behaviors (Adoption)

We will be able to detect changes of 13.0% to 29.5% in self-reported fruit and vegetable intake, urine sodium and potassium, and home-prepared dinners per week. These differences are smaller in magnitude than actual differences observed in prior trials.^{29,30}

Analysis Plan (RE-AIM Framework)

Reach. As in prior work, we will quantify recruitment yields and engagement. 52,53

Effectiveness & Adoption. The analysis will be conducted by the Statistical Core under the intent-to-treat principle for both effectiveness and adoption endpoints. The residual distribution of all outcomes will be checked for normality and log-transformed where appropriate. For the Primary Aim, we will use generalized estimating equation (GEE) models with a treatment-by-visit interaction term. The visit term will be used to compare changes on office SBP between 3 months versus baseline, 6 months versus 3 months, and 6 months versus baseline with a product (interaction) term to compare changes across intervention assignment (DASH vs self-directed shopping). Models will be adjusted for ZIP code or baseline BP in sensitivity analyses. Continuous variables will be analyzed with a Gaussian distribution, identity link, while dichotomous variables will be analyzed with a binomial distribution, logit link.

Implementation. Quality-of-life and cost data will be used to analyze health economic data and budget impact, based on cost per HTN case prevented and 10-year cost per quality-adjusted life-year gained.

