#### 1 Introduction

GoFreshRx is an individual level, randomized feeding trial to determine the effect of 12 weeks of dietitian-assisted DASH-patterned grocery shopping on seated blood pressure in 150-176 adults in the ages of 18-100 years who are actively taking a stable dose of blood pressure medications. Participants are randomly assigned to one of 2 groups: (1) Dietitian-assisted, DASH-patterned grocery shopping or (2) Self- directed grocery shopping group. The trial is organized into two phases: the intervention phase (assessed at 3 months) and the observation (maintenance) phase with physical assessments at 6-months and behavioral assessments at 6 and 12 months. The primary trial analysis described in this document focuses on physical assessments at 3 and 6 months. Other outcome assessments performed during the study (i.e., qualitative interviews as well as questions related to quality of life, grocery shopping and dining habits, and perceived stress) are not planned as part of this analysis.

The primary outcome is the net effect of DASH groceries with reduced sodium, DASH-patterned groceries versus self-directed grocery shopping on 12-week seated systolic blood pressure (as measured at 3 months, the end of the intervention phase).

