#### 1.1 Primary aim

To determine the effects of 12-weeks of dietitian-assisted, home-delivered, virtually-ordered, low sodium, DASH groceries compared with self-directed grocery shopping (DASH education and a \$500/month stipend over 3 months) on seated office systolic blood pressure among Black adults with treated stage 1 or stage 2 hypertension.

In this randomized controlled trial (RCT) of at least 150 participants, we will compare the DASH grocery intervention versus the self-directed group over 12 weeks to determine its effect on seated systolic blood pressure.

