#### 3.3 Power and sample size

The primary outcome is change in SBP between the two randomized assignments. Our power calculation is based on the 12-week means and variances from the DASH-Sodium trial, where the 12-week between-group difference in SBP was -8.9 mm Hg. With 75 people in each arm, we will have sufficient power to detect a difference in SBP of -5.8 mm Hg (type 1 error of 0.05, power of 0.85; assuming a standard deviation of 11.85 and 11.4 for control and intervention groups based on the DASH-Sodium trial). We will over-recruit up to at least 176 participants to account for a 15% attrition rate.

With respect to secondary endpoints, we will have sufficient power to detect small differences of 15% or less in the following secondary endpoints: wake-time SBP, BMI, cholesterol, triglycerides, and hemoglobin A1c. Regarding adherence, we will be able to detect changes of 13.0%–29.5% in self-reported fruit and vegetable intake, urine sodium and potassium, and 24-hour recall potassium. These differences are smaller in magnitude than the actual differences observed in prior trials.

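### Protocol section 4 gives 150 as the number randomised, but the power calculation needs 150 analysed; if only 150 were randomised, power at 5.8 mm Hg would be about 80%, not 85%

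*Protocol*

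**What the plan says.** The documents give the sample size in two ways.

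**150, or a range starting at 150.** Protocol section 4 (Overview of Design): "we will randomly assign 150 Black adults with treated stage 1 or 2 HTN". Protocol section 13 (Analysis): "The trial has sufficient resources to enroll 150-176 participants who will be randomly allocated to 1 of 2 sequences". SAP section 1 describes the effect "on seated blood pressure in 150-176 adults in the ages of 18-100 years". SAP section 1.1: "In this randomized controlled trial (RCT) of at least 150 participants".

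**176, with an attrition allowance.** Protocol section 6, recruitment strategies: "We will implement a variety of strategies to achieve our recruitment target, i.e., ~176 participants". Protocol section 6, recruitment of women and Black adults: "We will recruit 176 participants, anticipating a potential 15% attrition rate". SAP section 3.3: "We will over-recruit up to at least 176 participants to account for a 15% attrition rate".

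Protocol section 13 and SAP section 3.3 both attach the power claim to 75 per arm: power 0.85 for a 5.8 mm Hg difference in office SBP at a type 1 error of 0.05. SAP 3.3 adds the standard deviations, 11.85 (control) and 11.4 (intervention).

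**The concern.** The same 150 plays two roles. In the power calculation it is the number contributing outcome data. In Protocol section 4 it is the number randomised, and in three other places it is the bottom of an acceptable range. Under the trial's own 15% attrition it cannot be both. The sentences that speak of random assignment or allocation give 150 or 150-176, whereas those that give 176 alone speak of recruiting or over-recruiting. A reader therefore cannot tell from the text which randomised number completes enrolment, or which number the 85% belongs to. SAP 3.3 does not settle it, because its wording of the 176 reads as both a ceiling and a floor.

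At stake is whether the advertised power holds over the whole stated range of sample sizes.

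**Working it through.** **Inputs.** Difference 5.8 mm Hg, SDs 11.85 and 11.4, 75 per arm, power 0.85 and 15% attrition (SAP 3.3); two-sided 5% test (SAP 3.2); 1:1 allocation (SAP 3.1).

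**Pooled SD.** √[(11.85² + 11.4²)/2] = √[(140.42 + 129.96)/2] = 11.63.

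**Power, normal approximation.** Φ(Δ/SE − 1.96), with SE = 11.63 × √(2/n) and n the number analysed per arm. The t column in the table is the noncentral-t version.

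**Step 1: reproduce the stated figure.** With n = 75, SE = 1.899, 5.8/1.899 = 3.055, and Φ(1.095) = 0.863 (noncentral t: 0.859). Using 11.85 in both arms gives 0.850. The stated 0.85 is reproduced.

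**Step 2: check the inflation.** 150/(1 − 0.15) = 176.5, against 176 stated. In reverse, 176 × 0.85 = 149.6. So 150 is the post-attrition number and 176 is the number before attrition.

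**Step 3: apply the same attrition to 150 randomised.** 150 × 0.85 = 127.5, or 63.75 per arm. SE = 2.059, 5.8/2.059 = 2.816, and Φ(0.856) = 0.804 (noncentral t: 0.798). With 11.85 in both arms it is 0.789.

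**Step 4: detectable difference at 85% power.** (1.960 + 1.036) × SE. For n = 63.75 this is 2.996 × 2.059 = 6.17 mm Hg (noncentral t: 6.22). For n = 75 it is 5.69 mm Hg (noncentral t: 5.73).

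| Randomised | Loss | Analysed per arm | Power at 5.8 (normal / t) | Detectable at 85% (t) |
|---|---|---|---|---|
| 150 | none | 75 | 0.863 / 0.859 | 5.73 |
| 176 | 15% | 74.8 | 0.862 / 0.858 | 5.73 |
| 150 | 15% | 63.75 | 0.804 / 0.798 | 6.22 |

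**Step 5: how much loss 150 could absorb.** By the normal approximation, 85% power at 5.8 mm Hg needs 73 per arm, or 146 in total. From 150 randomised, that leaves room to lose 4 people.

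**The case against.** The best reply is that this is labelling, not a design fault. The arithmetic in the power section is sound. The Protocol has its own attrition allowance in section 6, and SAP 3.3 repeats it. Section 13 speaks of resources, which is a statement of capacity, and both the 150-176 range and a minimum of 150 are compatible with randomising 176. Only Protocol section 4 gives 150 as a single randomised number. All of that stands, and it makes 176 the likely intent. It does not make section 4 right, and it does not tell a reader of section 13 or SAP 1 and 1.1 that the lower limit carries less power.

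Three stronger readings are tempting, and the documents do not support them.

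- A reader might infer that the 85% was miscalculated. It was not: it is stated for 75 per arm and reproduces there.
- A reader might infer that stopping at 150 randomised would satisfy the plan. It would fit Protocol sections 4 and 13 and SAP 1 and 1.1, but not the 176 in Protocol section 6 or SAP 3.3, and no section makes 150 a stopping point.
- A reader might infer that the trial's real power is 80%. The calculation compares 3-month means, while SAP 3.2 plans a GEE with a treatment-by-visit interaction. The documents give no correlation between baseline and follow-up. As an illustration only, with equal SDs at both visits and 63.75 per arm, a change-score comparison has power of about 0.73, 0.80 and 0.88 at assumed correlations of 0.4, 0.5 and 0.6.

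It may also be said that power at the 8.9 mm Hg seen in DASH-Sodium stays near 99% (0.990) even at 63.75 per arm. That is true. But the plan chose 5.8 mm Hg as its detectable difference, and Protocol section 3 reports that the prior dietitian-assisted grocery studies did not significantly affect clinical outcomes such as BP.

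**Conclusion.** Protocol section 4 is wrong as written: randomising 150 does not deliver the stated power once the plan's own attrition is applied. The lower limit in Protocol section 13 and SAP 1 and 1.1 has the same weakness. The severity is modest. If 150 were randomised, the loss would be about 6 points of power at 5.8 mm Hg (0.859 to 0.798), or about 0.5 mm Hg in the detectable difference (5.73 to 6.22). If 176 are randomised, nothing is lost.

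This rests on the SAP's SDs, on 15% attrition counted from randomisation and equal in the two arms, and on the documents' simplified two-sample calculation. The allowance makes sense only if 176 counts people randomised, although the text says recruited. SAP section 3.4 (Sensitivity analyses) also keeps out-of-window measurements out of the primary analysis, and the documents do not say whether the 15% covers these.

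**What to change.** State one randomisation target in Protocol sections 4 and 13 and SAP sections 1, 1.1 and 3.3, consistent with Protocol section 6: 176 randomised, 88 per arm, with about 150 (75 per arm) expected in the analysis. Label 150 as the expected analysed number wherever it appears, and reword the over-recruitment sentence in SAP 3.3 so that 176 is clearly a target, a minimum or a maximum.

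If the 150-176 range is to be kept, add the power at its lower end after 15% attrition: about 0.80 at 5.8 mm Hg, or about 6.2 mm Hg detectable at 0.85. Say that these figures come from a two-sample comparison rather than from the GEE.

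The cost is wording in five sections. With 176 as the target, no procedure, analysis or power claim changes. Keeping the range means publishing a slightly less favourable power figure.
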